#### **D.5. Randomized Control Trial of the BI, Messaging, and Website Extenders (Aim 3) [Months 13 – 24]**

**a. Overview.** We plan a pilot study to assess the feasibility and acceptability of the BI and website, to obtain preliminary evidence of BI efficacy (on alcohol use and sex behavior outcomes), and to determine feasibility of procedures (e.g., enrollment, BI and website exposure, follow-up rates) for a future RCT.

**b. Design.** We plan a 2 (interventions) x 2 (baseline, follow-up) design. Women will be randomized, complete baseline, receive intervention (BI or brochure), post-survey (BI arm only), and 3-month follow-up. Measures will assess IMB constructs, alcohol, and sexual behavior, and STIs. Rationale for control: We chose a brochure because it is a science-based (CDC and NIAAA material) alternative that is representative of what clinics currently provide.

**c. Sample** ( $n=50$ ) was based on published guidelines for treatment development research, which recommend 15-30 per cell for Phase IB research. This also aligns with NIH expectations for R34 research. We recognize that the trial is not adequately powered to detect between-group differences, but it can clarify the potential of the intervention and suggest effect sizes (ES). We also know that ES estimates will have large standard errors. We primarily aim to find a pattern of results that is supportive of the experimental treatment.

**d. Participants.** We will recruit 50 women using screening, eligibility, recruitment, and consent procedures described in D.1.c. Women who participated in Aim 1 or 2 will not be eligible.

**e. Baseline.** Participants will complete the CASI on a tablet computer. Measures included in the CASI are listed in Table 2; the measures are reliable and valid, and have been used in prior research with young women. The CASI will take ~45 mins, and will assess background variables, outcomes, mediators, and moderators.

The self-report **outcomes** include sexual behavior; alcohol use; and the co-occurrence of sex and alcohol.

Consistent with PA-13-078, we will assess hypothesized **mediators** and **moderators**. We recognize that we will not have sufficient statistical power to test mediation or moderation in this pilot. However, we will evaluate short-term intervention effects on the hypothesized intervening variables, to determine if they have promise as potential mediators for a subsequent RCT.

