To determine **feasibility** of the BI and of an RCT, we will calculate the percentage of individuals who were: eligible; consented; attended their intervention; accessed the website; and returned for the follow-up. Based on previous research, we expect  $\geq 90\%$  of those assigned to a BI to attend their intervention. Based on our recent trials (R01-MH068171), we expect  $\geq 80\%$  of all women to return for the 3-month follow-up.

To determine **acceptability** of the BI, messaging and website, we will calculate Ms for the satisfaction surveys, and inspect responses. We **predict** that the intervention materials will be well-accepted, as shown by mean ratings  $\geq 4$  on a 5-point Likert scale. To further evaluate the **acceptability** of the messaging and website, we will collect use metrics (e.g., timing and frequency of website access, number of clicks on links for information, video view time). We **predict**, and will construe as acceptable, if women receive messages, link to the website, and view videos all the way through/multiple times.

To obtain preliminary evidence of BI **efficacy**, repeated measures ANOVAs will test intervention and time effects on the primary outcomes (alcohol use frequency, quantity, binge frequency; condom use, number of sexual partners; alcohol use before sex). We **hypothesize** an intervention x time interaction for all outcomes; thus, we **hypothesize** that BI recipients but not controls will reduce alcohol use and alcohol use before sex, increase proportion of protected sex, reduce condom use problems and number of partners.

To prepare for a future trial, we also provide preliminary data on mechanisms of action by testing intervention effects on **hypothesized mediators** (e.g., IMB constructs, attitudes, norms, self-efficacy).

**j. Effect sizes and power.** We recognize that effect size estimates based on small samples often have large SDs and wide confidence intervals (CIs). We also acknowledge that we will not have power to detect statistically significant results. Nonetheless, pilot data are useful to gauge whether BI effects are encouraging, to examine distribution of outcome variables, to inform future analytic approaches, and to suggest the range of effect sizes that are reasonable to expect in a future trial. Thus, the focus of our analyses will not be on strict significance testing but on estimating effect sizes and CIs.

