## Data Analyses Plan

For the feasibility data, we produced a Consort flow figure and calculated summary statistics to report the findings. For the acceptability data, we calculated summary statistics and identified illustrative quotes from the semi-structured interviews. Prior to analyzing the efficacy data, we used t-test and chi-square analyses to determine if randomization produced equivalent groups with respect to demographic characteristics and outcome measures.

For the efficacy data, we used inferential statistics to compare the two conditions to one another. Specifically, we used generalized estimating equations (GEE; Hardin & Hilbe, 2013) to examine the impact of the intervention on primary outcomes (i.e., typical drinks per week, maximum drinks per day, number of heavy episodic drinking days, alcohol-related consequences, number of sexual partners, and alcohol use before sex) as well as to model change over time. We used an intent-to-treat approach such that data from all women were used. We hypothesized an intervention-by-time interaction such that participants in the BI, but not the control, condition would reduce alcohol use and sex risk behavior over time. All analyses examined the impact of time (baseline vs. follow-up), intervention condition (control vs. BI), and the time-by-condition interaction controlling for age. When interactions were not significant, models were run without the interaction terms. Count variables (i.e., drinks per week, maximum drinks per day, heavy episodic drinking days, number of partners, drinks before sex) were analyzed using a Poisson distribution unless otherwise indicated. Alcohol consequences were analyzed using linear models.

For condomless sex, a GEE model could not be fit due to significant over-dispersion bounded by a large number of zeroes. Instead, a zero-inflated negative binomial model was chosen based on the (a) lower AIC and BIC values in the negative binomial versus Poisson models, and zero-inflated versus non-inflated models; and the (b) likelihood ratio test comparing zero-inflated Poisson and negative binomial models (lr test:  $\chi^2(1) = 60.76, p < .001$ ) (Long & Freese, 2006). Further, a zero-inflated model is considered particularly appropriate for sexual health research, such as condomless sex (He, Tang, Wang, & Crits-Cristoph, 2014), given that some mechanisms responsible for zero counts in the data differ from

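### The Poisson GEE for five primary counts in about 50 women states no variance estimator, scale or small-sample correction; even an ordinary robust standard error is modestly too small at this size

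*SAP*

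**What the plan says.** The SAP's Data Analyses Plan uses GEE for the primary outcomes, with terms for time, condition, their interaction and age. The five counts "were analyzed using a Poisson distribution unless otherwise indicated", and no exception is then indicated for any of them. The text does not name a working correlation, a variance estimator (model-based or robust), a scale parameter or a small-sample correction. If the interaction is not significant, it is dropped and the model is refitted.

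Dispersion is discussed for one outcome only. For condomless sex, "a GEE model could not be fit due to significant over-dispersion bounded by a large number of zeroes", and a zero-inflated negative binomial model was used after comparing AIC, BIC and a likelihood ratio test (chi-square 60.76 on 1 df).

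The protocol (D.5.b to D.5.d) sets the size and shape: "We plan a 2 (interventions) x 2 (baseline, follow-up) design" and "We will recruit 50 women using screening, eligibility, recruitment, and consent procedures described in D.1.c". Section D.5.i expects at least 80% "of all women to return for the 3-month follow-up". Section D.5.j says that "the focus of our analyses will not be on strict significance testing but on estimating effect sizes and CIs".

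**The concern.** A Poisson model sets the variance equal to the mean. Self-reported drinking and partner counts often vary more than that, and eligibility (protocol D.1.c) admits both a woman with a single day above three drinks and a woman who drinks heavily every week. If the standard error takes the Poisson variance at face value, extra variation is ignored and intervals are too narrow.

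A robust standard error does not depend on the Poisson variance being right. It is, however, biased downwards when there are few independent units, and here there are about 50 women with at most two observations each.

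Two results depend on this standard error. One is the confidence interval around each effect size, which the protocol makes the focus of the pilot. The other is the decision to keep or drop the interaction. Low power does not cover the point: it is a reason to expect wide intervals, and a standard error that is too small makes them look narrower than they are.

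**Working it through.** **Inputs from the documents.** 50 women, so about 25 per arm; two time points; at least 80% followed up, so about 0.80 × 50 = 40 women with both; five mean parameters (intercept, time, condition, interaction, age). The sample size comes from a guideline "which recommend 15-30 per cell for Phase IB research", not from a power formula: 2 × 15 to 2 × 30 is 30 to 60, and 50 lies inside. The one dispersion statistic given also checks: 60.76 on 1 df gives p of about 6 × 10⁻¹⁵, in line with the stated p < .001.

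**Assumed inputs.** The documents give no mean, SD, dispersion or within-woman correlation for the five counts, and no alpha. Assumed: mean 2 to 8, variance/mean ratio φ from 0.5 to 10, two-sided 5%, and a component shared between each woman's two visits in the over-dispersed scenarios.

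**Approximation for a fixed-scale standard error.** If the true variance is φ times the mean and the scale is held at 1, then SE used / true SE ≈ 1/√φ, and the false-positive rate ≈ 2 × [1 − Φ(1.96/√φ)], where Φ( ) is the normal distribution function.

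| φ | 1/√φ | false-positive rate |
|---|---|---|
| 0.5 | 1.41 | 0.6% |
| 1 | 1.00 | 5.0% |
| 1.5 | 0.82 | 11.0% |
| 2 | 0.71 | 16.6% |
| 4 | 0.50 | 32.7% |
| 5 | 0.45 | 38.1% |
| 10 | 0.32 | 53.5% |

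**Simulation.** 25 per arm, no true interaction, 80-100% follow-up, log-link Poisson GEE with exchangeable correlation, 1,500 to 2,000 trials per scenario. Each cell gives the false-positive rate for the interaction, then the median SE divided by the true SD of the estimate. All columns use a normal reference.

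| mean, φ | fixed scale 1 | Pearson-scaled | robust, uncorrected | Mancl-DeRouen |
|---|---|---|---|---|
| 5, 0.5 | 0.7%, 1.41 | 5.0%, 1.00 | 5.3%, 0.97 | 4.3%, 1.02 |
| 8, 1 | 5.4%, 1.01 | 5.5%, 1.00 | 6.3%, 0.97 | 5.1%, 1.02 |
| 8, 2 | 17.3-17.5%, 0.71 | 5.5-5.9%, 0.99 | 5.8%, 0.97-0.98 | 4.6-4.8%, 1.02 |
| 8, 5 | 36.8-41.7%, 0.43-0.46 | 5.6-7.7%, 0.93-1.00 | 5.8-6.8%, 0.92-0.98 | 4.9-5.5%, 0.96-1.02 |
| 8, 10 | 53.7%, 0.31 | 8.0%, 0.92 | 7.9%, 0.92 | 6.6%, 0.97 |
| 2, 1.5 | 11.4%, 0.80 | 6.1%, 0.97 | 7.0%, 0.94 | 5.9%, 0.99 |
| 2, 2 | 18.0%, 0.69 | 6.8%, 0.94 | 7.3%, 0.92 | 6.5%, 0.97 |
| 2, 4 | 33.1%, 0.49 | 8.1%, 0.91 | 8.3%, 0.89 | 6.9%, 0.94 |

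The fixed-scale column agrees with the approximation. Monte Carlo error near 5% is about ±1 point (1.96 × √(0.05 × 0.95/1500) = 0.011), so a single rate of 5.3% or 5.8% does not differ from 5%. The evidence on the uncorrected robust standard error is that its ratio was below 1 in every scenario (0.89 to 0.98), including those without over-dispersion, and that the rate was highest when counts were sparse or strongly skewed.

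**Effect of adding a t reference.** Two further simulations used Mancl-DeRouen with a t reference. With assumed mean 2-8 and φ 1-8, the rates were 6.2-8.0% for uncorrected robust and 4.4-5.3% for corrected. With assumed mean 4-10 and negative binomial dispersion 0.6-1.5, they were 7.3-8.3% and 5.4-6.2%.

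**Cost in width.** The typical Mancl-DeRouen to robust ratio is 1.02/0.97 = 1.05. With 50 − 5 = 45 df the t multiplier is 2.014 in place of 1.96, a factor of 1.03. Together, 1.05 × 1.03 ≈ 1.08.

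**The case against.** The strongest reply is that nothing here shows the reported standard errors to be wrong. Several parts of it stand.

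- A reader might infer that the five counts are over-dispersed because condomless sex was. The documents do not support that. They tie the condomless-sex problem to excess zeros, partly from women with no sexual activity, and that mechanism does not carry over to drinks per week among women enrolled for at-risk drinking. Partner counts or maximum drinks could be equi- or under-dispersed, and a fixed-scale standard error would then be right or too large.
- A reader might infer that up to half of null interactions would be declared significant. That needs both a fixed-scale standard error and strong over-dispersion. The SAP states neither.
- The SAP is silent on corrections, which is not a statement that none was used. A Pearson-scaled standard error, another ordinary choice, gave 5.5-8.1% for φ from 1 to 10. The re-expression of five outlying values would also lower dispersion somewhat, although the variables are not named.
- The protocol concedes the pilot's limits: "We recognize that the trial is not adequately powered to detect between-group differences". It also warns of wide intervals.

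The objection does not dispose of the point. The most sensible way to fill the gap, an ordinary robust standard error, is still slightly too small with this many women, whatever the dispersion. The range of permitted readings also runs from a trivial error to a severe one, so a reader cannot tell how far to trust the intervals.

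**Conclusion.** The point holds as a worthwhile, inexpensive improvement. With an uncorrected robust standard error, the interaction standard error is about 2-11% too small and the false-positive rate about 5-8%, because there are few clusters. With a fixed-scale model-based standard error, the result depends on dispersion that the documents do not report: about 20-70% too small, with false-positive rates of about 11-54%, for φ from 1.5 to 10; correct at φ = 1; too large below 1.

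It should not be read as a finding that the drinking and partner counts are over-dispersed, that both common standard errors are always too small, or that the intervals already produced are wrong. All sizes rest on the assumed means, dispersions and correlations, on a two-sided 5% level, and on about 25 women per arm with at least 80% follow-up. The pilot's emphasis on estimation lowers the stakes but does not remove them, since the intervals and the interaction-dropping rule both use this standard error.

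**What to change.** Add to the SAP, for the count GEEs: the working correlation; a robust covariance with a small-sample bias correction (for example Mancl-DeRouen or Kauermann-Carroll); a t reference, for example with the number of women minus the number of mean parameters as degrees of freedom; and a statement that fixed-scale Poisson standard errors are not used. Report the dispersion of each of the five counts. A negative binomial GEE as a sensitivity analysis is optional.

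State which standard error was used in the analysis. Re-issue the confidence intervals and interaction tests only if it was an uncorrected robust or a fixed-scale one.

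The cost is a sentence or two in the SAP, possibly a re-run, and intervals about 8% wider than those from an uncorrected robust standard error with a normal reference. The correction is not perfect: without the t reference, rates of 6-7% remained for sparse or very skewed counts.

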the traditional regression model. For example, women who are not engaging in any sexual activity will produce zero counts in a condomless sex outcome, no matter how they vary on other predictors, and are therefore considered to be structurally different (in statistical modeling terms) than women who are at-risk of engaging in condomless sex but do not do so. Outliers ( $z$  scores  $\geq 3.29$ ; 3 cases at baseline and 2 at follow-up) were re-expressed to the next highest value (Tabachnick & Fidell, 2007).

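### Condomless sex: the zero-inflated model that replaces GEE names no method for the two correlated rows per woman, so its confidence intervals may have the wrong width

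*SAP*

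**What the plan says.** Protocol D.5.b sets a two-arm design with each woman measured at baseline and at three months. For the efficacy models the SAP states: "All analyses examined the impact of time (baseline vs. follow-up), intervention condition (control vs. BI), and the time-by-condition interaction controlling for age". It adds: "When interactions were not significant, models were run without the interaction terms".

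The listed outcomes are analysed by GEE, which allows for repeated measures on the same woman. Condomless sex is the exception: "For condomless sex, a GEE model could not be fit due to significant over-dispersion bounded by a large number of zeroes". The text continues: "Instead, a zero-inflated negative binomial model was chosen". The reasons given are lower AIC and BIC, a "likelihood ratio test comparing zero-inflated Poisson and negative binomial models" (chi-square 60.76 on 1 degree of freedom), and the argument that some zeros are structural. Outliers "were re-expressed to the next highest value". The SAP mentions no random effect, clustered variance, bootstrap or other device for the pairing in this model.

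Protocol D.5.j puts the weight on effect sizes and confidence intervals rather than significance tests, and wants a plausible range of effects for a later trial.

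**The concern.** The reasons for the ZINB are all about the shape of the distribution. Over-dispersion and excess zeros are one problem, and correlation between a woman's two counts is another. Changing the model to solve the first removed the only stated answer to the second.

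A ZINB fitted by ordinary maximum likelihood treats each row as a separate woman. With positive correlation this distorts the two reported terms in opposite directions. The interaction is a within-woman contrast, so its interval becomes too wide. The condition effect in the reduced model averages a woman's rows, so its interval becomes too narrow. The SAP's rule links the two: an over-wide interaction interval makes it more likely that the interaction is dropped, which leads to the over-narrow condition interval.

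Interval width is a stated product of this pilot. Condomless sex is also the SAP's only condom outcome, and the protocol (D.5.i) counts condom use among its "primary outcomes (alcohol use frequency, quantity, binge frequency; condom use, number of sexual partners; alcohol use before sex".

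**Working it through.** **Inputs from the documents.** 50 women (Protocol D.5.c and D.5.d) and at least 80% return expected (D.5.i), so 50 + 0.8 × 50 = 90 rows at 80%. Model terms are time, condition, their interaction and age (SAP).

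**The SAP's own figure.** The upper tail of chi-square(1) at 60.76 is 6.4 × 10⁻¹⁵, or half that (3.2 × 10⁻¹⁵) with the boundary correction. This agrees with the stated p < .001. The statistic cannot be rebuilt without data. It is large enough that negative binomial over Poisson is unlikely to change, and that choice is not disputed here.

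**Direction, in closed form.** Take two rows per woman with equal variance σ² and correlation ρ.

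- A within-woman change has true variance 2σ²(1 − ρ). Independent rows give 2σ². Model SE / true SE for the interaction = 1/√(1 − ρ).
- A woman's mean has true variance σ²(1 + ρ)/2. Independent rows give σ²/2. Model SE / true SE for condition without the interaction = 1/√(1 + ρ).

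**Size, by simulation.** The following are assumed, because the documents do not give them: 25 women per arm, no true effect, a constant inflation part, and counts and structural zeros paired through a Gaussian copula. The ratio is the root mean square model SE divided by the SD of the estimates.

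- Simulation A: 40 follow-up rows, outliers re-expressed as in the SAP, 2,000 replicates per cell. The four settings (at-risk mean, NB size, structural zeros) were (5, 1, 25%), (5, 0.7, 40%), (8, 2, 40%) and (15, 6, 25%). They were chosen so that the median likelihood ratio was 56–70, near 60.76. Monte Carlo error of a ratio is about 0.02.
- Simulation B: means 12 or 20, dispersion 1.2 or 2.0, structural zeros 20% or 40%, return 90% or 80%, 1,500 runs per setting (at most 64 discarded).

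| Model SE / true SE, independent rows | ρ = 0 | 0.3 | 0.5 | 0.7 |
|---|---|---|---|---|
| Interaction, closed form | 1.00 | 1.20 | 1.41 | 1.83 |
| Interaction, A | 0.92–0.95 | 0.98–1.06 | 1.06–1.19 | 1.16–1.36 |
| Interaction, B | 0.93–0.94 | 0.98–1.00 | 1.06–1.10 | 1.19–1.29 |
| Reduced-model condition, closed form | 1.00 | 0.88 | 0.82 | 0.77 |
| Reduced-model condition, A | 0.97–0.99 | 0.88–0.92 | 0.83–0.90 | 0.80–0.82 |
| Reduced-model condition, B | 0.96–1.00 | 0.88–0.91 | 0.83–0.86 | 0.77–0.81 |

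In the simulations ρ is latent. Latent 0.3 / 0.5 / 0.7 gives observed correlations of about 0.2 / 0.3 / 0.5. That, and a small-sample shortfall in the ZINB standard error (0.92–0.95 at ρ = 0), explains why the interaction ratios fall below the closed form. At 150 per arm the interaction ratios are 1.23 and 1.44 at latent 0.5 and 0.7 (observed 0.36 and 0.55). The closed form at those observed values gives 1/√0.64 = 1.25 and 1/√0.45 = 1.49.

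**Coverage of a nominal 95% interval** (B, main setting, latent 0.3 / 0.5 / 0.7): interaction 94.6% / 97.0% / 98.8%; condition 91.5% / 89.6% / 87.3%.

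**Example** (at-risk mean 5, latent 0.5, rate ratio 1):

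- Interaction: true SE 0.44, so exp(±1.96 × 0.44) = 0.42 to 2.37. Independent rows: 0.44 × 1.17 = 0.515, giving 0.36 to 2.74.
- Condition: true SE 0.31, giving 0.54 to 1.84. Independent rows: 0.31 × 0.86 = 0.267, giving 0.59 to 1.69.

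**The case against.** The strongest reply is that this is a reporting gap. The SAP nowhere says that rows were treated as independent, and clustered standard errors are easy to request and easy to leave out of a write-up. That stands: what is established is an unspecified method, and the interval errors are conditional on an independent-row fit.

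One could also read the replacement as a follow-up-only model adjusted for baseline, which would remove the problem. The SAP does not describe such a model, and it conflicts with the statement that all analyses contain time and time-by-condition.

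On materiality, the hypothesised interaction is about right at low correlation and errs on the cautious side above that. The over-narrow interval belongs to a term that mixes baseline with follow-up and is not the hypothesised effect. In the example all four intervals are wide and no conclusion would change. The protocol already admits low power and wide intervals, and its condom hypothesis concerns the proportion of protected sex, not a count of condomless acts. These points limit the weight of the concern. They do not remove it, because the SAP prescribes the reduced model and the protocol makes the intervals a product of the pilot.

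Last, clustered variance is imperfect with 50 women. In simulation B, with only the factor 50/49, it covered 90–93%. For the interaction at latent 0.3 that is worse than independent rows. The remedy therefore needs a small-sample correction.

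**Conclusion.** The concern holds. For condomless sex the SAP drops its only named method for paired data and names no other. Followed literally, it gives an independent-row fit. With positive within-woman correlation the interaction interval is then too wide at moderate to high correlation: the standard error is about 1.1–1.2 times the true one at latent 0.5 and 1.2–1.4 times at 0.7. The reduced-model condition interval is too narrow, at about 0.9 times at latent 0.3 and about 0.8 times at 0.7.

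The directions follow from the design. The sizes rest on assumed correlation, mean, dispersion and zero share. Since neither the variance method nor the pre-post correlation is given, a reader cannot tell whether the interval is right. This should be corrected, but it concerns one model in a pilot and does not undermine the trial.

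**What to change.** State in the SAP how the ZINB handled the two rows per woman. If nothing was done, refit it with participant-level variance that allows for about 50 women: variance clustered on woman with a small-sample correction, a woman-level bootstrap or jackknife, or a participant random intercept. The choice is the trial statistician's. Re-report the interaction with its 95% interval, and the reduced-model condition effect if it was used.

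In simulation A, clustered variance with the factor (50/49)(N − 1)/(N − k), where N is rows and k parameters, gave ratios of 0.95–1.02 (interaction) and 0.93–1.00 (condition) at latent 0.3–0.7.

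The cost is one sentence and at most one refit, with no new data. With clustered variance the median condition interval became 0.99–1.25 times as wide and the interaction interval 0.73–0.95 times.

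As a separate clarification, say whether condomless sex is primary. The protocol lists condom use as primary, but the SAP's list, which ends with "alcohol-related consequences, number of sexual partners, and alcohol use before sex", has no condom outcome.

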| 
 
offer gender-tailored education about blood alcohol concentration (BAC); social, health, sexual risks associated with binge drinking; safe drinking guidelines
 
  | 
 
Correct exaggerated peer norms
 
Develop discrepancy between self-other
 
   |
| 
 
offer gender-tailored education about blood alcohol concentration (BAC); social, health, sexual risks associated with binge drinking; safe drinking guidelines
 
  | 
 
Change attitudes about drinking with accurate information about effects of alcohol on women
 
Develop discrepancy between current & possible self
 
Provide benchmark for reduced drinking/goal setting
 
                                |
| 
 
offer gender-tailored education about risk for HIV/STIs from unprotected sex with multiple partners or partners who are not mutually monogamous; safe sex guidelines
 
                                      | 
 
Provide accurate information about risk of STIs for women, how/why condom use and mutual monogamy protects health; change attitudes about risk reduction
 
Develop discrepancy between current & possible self
 
                                |
| 
 
discuss readiness guides for changing alcohol and sexual behavior
 
   | 
 
Develop discrepancy between real-desired self
 
Cultivate change talk
 
   |
| 
 
identify alcohol and/or sexual risk reduction goals (e.g., drink less or not at all [when/where/with whom], use condoms all the time with partner X, negotiate more effectively with a resistant partner)
 
 | 
 
Goal-setting enhances motivation
 
Generate change talk and/or commitment language, establishing behavioral intention
 
   |

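### The zero-inflated model for condomless sex comes with no overall arm-by-time effect, and neither of its coefficients alone estimates the BI effect on mean condomless acts

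*SAP*

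**What the plan says.** The SAP's single section, Data Analyses Plan, analyses the efficacy outcomes by GEE, with a Poisson distribution for most counts. The hypothesis is an intervention-by-time interaction in which "participants in the BI, but not the control, condition would reduce alcohol use and sex risk behavior over time". The model terms are given once for all outcomes: "All analyses examined the impact of time (baseline vs. follow-up), intervention condition (control vs. BI), and the time-by-condition interaction controlling for age". Interactions that are not significant are then removed.

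Condomless sex is the exception: "For condomless sex, a GEE model could not be fit due to significant over-dispersion bounded by a large number of zeroes". The SAP continues: "Instead, a zero-inflated negative binomial model was chosen based on the (a) lower AIC and BIC values", and adds a likelihood ratio test of zero-inflated Poisson against ZINB, χ²(1) = 60.76. It motivates the zero class by noting that "women who are not engaging in any sexual activity will produce zero counts in a condomless sex outcome", and distinguishes these women from at-risk women who happen to have no condomless sex.

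The SAP does not say whether condition and its interaction with time enter the count part, the zero part or both. Nor does it say which coefficient, joint test or combined quantity answers the hypothesis, or how the two visits per woman are handled in the ZINB.

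In the protocol, section D.5.i lists condom use among the primary outcomes and expects the BI to "increase proportion of protected sex, reduce condom use problems and number of partners". Section D.3.a makes a larger share of condom-protected acts a target of the BI, and Table 1 gives as an example of a goal: "use condoms all the time with partner X".

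**The concern.** A GEE with a log link gives one interaction: the ratio of change in the mean across all women. A ZINB with condition in both parts gives two, one for the mean count in a latent at-risk class and one for membership of the zero class. Neither is the change in mean condomless acts across all randomised women.

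The gap matters here because the intervention is meant in part to create zeros. A woman who becomes a consistent condom user with every partner reports zero. The class is latent and, as described, the model uses no indicator of sexual activity, so the fit can assign much of such a rise in zeros to the zero class. The stated rationale, absence of sexual activity, also fits baseline poorly, because eligibility (protocol D.1.c) requires recent sexual risk behaviour.

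Protocol D.5.j says the pilot is about estimating effect sizes and confidence intervals for a later trial. If the count-part ratio were read as the effect size, it could show nothing, or the wrong direction, while mean condomless acts fell. The rule for removing non-significant interactions adds to the uncertainty, since the SAP does not say how it applies to a two-part model.

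**Working it through.** **The SAP's own figure.** The upper tail of χ²(1) at 60.76 is 6.4 × 10⁻¹⁵ (3.2 × 10⁻¹⁵ if halved because the dispersion parameter is on its boundary), so p < .001 reproduces. The test supports negative binomial over Poisson among zero-inflated models. It does not test the need for zero inflation, for which the SAP cites AIC and BIC, and it does not bear on whether a GEE can be fitted.

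**Identity.** With π the structural-zero probability and μ the count-part mean, the overall mean is (1 − π) × μ. The arm-by-time ratio of overall means is therefore

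R = [arm-by-time ratio of (1 − π)] × [arm-by-time ratio of μ].

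The second factor is the exponentiated count-part interaction. It equals R only if the first factor is 1.

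**Assumed inputs.** The documents give no rates. Assumed: 30% structural zeros, μ = 15, dispersion 1, and each woman's underlying rate and structural-zero status the same at both visits. Age and loss to follow-up were not modelled.

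**30% of BI women move to zero at random.** Three of the four arm-by-visit cells have mean 0.70 × 15 = 10.5. For BI at follow-up, 1 − π = 0.70 × 0.70 = 0.49 and the mean is 0.49 × 15 = 7.35. So R = 7.35 / 10.5 = 0.70, the count-part ratio is 15 / 15 = 1.00, and the zero-part odds ratio is (0.51 / 0.49) / (0.30 / 0.70) = 2.43.

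**The lowest 30% of positive counts move to zero.** With dispersion 1 the count is geometric, with P(Y ≥ k) = (15/16)^k. Among positive counts, 1 − (15/16)^5 = 28% are 5 or fewer and 1 − (15/16)^6 = 32% are 6 or fewer, so counts of 1 to 6 become zero. The remaining mean is (15/16)^7 × (7 + 15) = 0.6365 × 22 = 14.00, giving R = 14.00 / 15 = 0.93. The mean of the positive counts rises from 16 to 22 (ratio 1.375), which pulls the count part above 1.

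**Fitted limits, 20,000 simulated women per arm** (maximum-likelihood ZINB):

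| Scenario at follow-up, BI arm | Overall R | Count ratio, terms in both parts | Zero-part odds ratio | Count ratio, intercept-only zero part |
|---|---|---|---|---|
| No effect | 1.009 | 1.006 | 0.992 | 1.007 |
| 30% to zero, random | 0.709 | 0.999 | 2.362 | 0.937 |
| Lowest 30% of positive counts to zero | 0.934 | 1.401 | 2.611 | 1.351 |
| Highest 30% of positive counts to zero | 0.329 | 0.449 | 2.173 | 0.405 |
| All acts cut by 30% | 0.699 | 0.698 | 0.993 | 0.698 |

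A repeat of the simulation gave 0.94 against 1.36 for low-count movers, and 0.94 (random) and 1.32 (low-count) with the intercept-only zero part.

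**Trial size.** With 25 per arm (an assumed equal split of 50) and 150 runs per scenario, the count part was above 1 while a Poisson GEE was below 1 in 71% of runs for low-count movers, 37% for random movers, 3% for the proportional cut and 14% under no effect. The GEE, with exchangeable correlation and robust standard errors, converged in all 4 × 150 = 600 runs, with more than 30% zeros expected.

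**The case against.** **The hypothesis is broad.** It speaks of reducing sex risk behaviour and names no mean ratio. A reader might infer that neither part of the ZINB tests it. The documents do not support that: moving to zero and having fewer acts are both reductions, each part tests a piece, and the SAP says the interaction was examined in every analysis. What stands is that no part alone, and no stated combination, estimates the overall effect.

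**The zero part sees what the count part misses.** Its odds ratio was 2.2 to 2.6 in all three move-to-zero cases. Setting the power of the count part alone against that of GEE would ignore half the model, so it is not used here. But an odds ratio for a latent class cannot be read as a change in mean acts.

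**Women at zero do not drop out of the count result.** A reader might infer that they do. A ZINB divides each zero by probability between the parts, and the SAP's wording places at-risk women without condomless sex on the count side. The distortion arises because excess zeros are largely absorbed by the zero part.

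**The split is an inference.** The SAP never says that condition enters the zero part, nor that the count ratio will be presented as the BI effect. True; but with an intercept-only zero part the single coefficient is still off.

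**GEE may really have failed.** Simulated convergence says nothing certain about data we cannot see. Over-dispersion and many zeros do not by themselves prevent a log-link GEE with robust variance, but an actual fitting failure cannot be excluded.

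**Choice of outcome.** The SAP's own list of primary outcomes omits condomless sex, and the protocol's hypothesis concerns the proportion of protected sex. So the mean number of acts is the natural summary of the count the SAP analyses, not a quantity the protocol defines.

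**Conclusion.** The point holds as a gap in what the ZINB analysis estimates. For condomless sex the SAP leaves the terms in each part unstated and specifies no overall arm-by-time effect, and the count coefficient is not a substitute for one when the BI changes the proportion of zeros.

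Illustratively, the count part can miss the effect (1.00 against 0.71) or point the wrong way (about 1.4 against 0.93–0.94). With an intercept-only zero part the corresponding figures are 0.94 and about 1.3.

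Reversal is not a general consequence: in these scenarios it appeared only when low-count women were the ones who moved. When high-count women moved, the direction was right (0.45 against 0.33), and a proportional cut gave no distortion. All sizes rest on assumed rates; the identity does not.

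The documents do not show that ZINB was the wrong model or that the reported GEE failure was mistaken. Making GEE the main analysis would be a trade-off, not a correction.

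**What to change.** 1. State which of time, condition, their interaction and age enter the count part and which enter the zero part, and how the rule for removing interactions applies to each.
2. Define the BI effect on condomless sex as the arm-by-time ratio of overall mean condomless acts across all randomised women. Compute it from the fitted ZINB as (1 − π) × μ by arm and visit, saying how age is averaged over.
3. Give it a confidence interval from a bootstrap that resamples women, keeping both visits of a woman together.
4. Present the count-part and zero-part coefficients as a description of how the change arose.
5. If it fits, show a log-link GEE with robust variance as a sensitivity analysis. If it does not, describe the failure.

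The cost is SAP wording and one further computation from a model already fitted, plus the sensitivity fit; no new data are needed. The downside is a wide interval in about 50 women, which protocol D.5.j already anticipates for all effect sizes in this pilot.
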